3.11 Analysis of Safety Endpoints

3.11.1 Adverse Events of Special Interest

3.11.1.1 Definitions & Derivations

An Adverse Event (AE) is any undesirable medical event occurring to a subject in a clinical trial, whether or not related to the trial medications.

Drug related AEs are AEs with a causality to drug being possibly, probably, definitely related or with a missing causality.

The only non-serious Adverse Events to be recorded are Adverse Events of Special Interest (AESIs). An AESI is the subset of an AEs that are due to:

- Dizziness or any other symptom or event possibly related to hypotension,
- Abnormality detected in laboratory assessments of sodium, potassium, uric acid, glucose, lipids, creatinine or eGFR,
- Symptom of pedal edema reported by the participant,
- Any other symptom or laboratory abnormality that led to treatment withdrawal.

AESI include events occurring during Run-in, Randomization Period and Follow-up.

A Serious Adverse Event (SAE) is any AE that meets one or more of the following criteria:

- Results in death;
- Is life-threatening;
- Requires in-patient hospitalization or prolongation of existing hospitalization;
- Results in persistent or significant disability/incapacity;
- Results in a congenital anomaly/birth defect.

Important medical events that may not result in death, be life-threatening, or require hospitalization may be considered serious when, based upon appropriate medical judgment, they may jeopardize the patient or subject and may require medical or surgical intervention to prevent one of the endpoints listed in this definition.

AESIs and SAEs will be recorded from time of informed consent up to 30 days after trial medication discontinuation.

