17.1.2. Adverse Event of Special Interest

The following AEs are considered AESIs and will be collected:

- Symptomatic hypotension: Dizziness or any other symptom or event possibly related to hypotension
- Abnormal laboratory findings of sodium, potassium, uric acid, glucose, lipids, creatinine or eGFR
- Headache
- Peripheral edema
- Any other symptom or laboratory abnormality that led to permanent discontinuation of trial medication.

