3.11.1.2 Adverse Event Summaries

For the summary of safety parameters, AEs will be classified according to the treatment period and treatment received as of the start date of the AE (Section 3.5.3). If an AE is ongoing at the time of randomization, it will be allocated to the Period 1 treatment. If a treatment ongoing at randomization worsens following randomization, the AE worsening will be allocated to the Period 2 treatment.

AESIs and SAEs will be classified according to the MedDRA (Medical Dictionary for Regulatory) system (version 24.0, March 2021) and summarized by system organ class and preferred term.

Treatment periods for AE summary include: Period 1/Run-in Period, Period 2, Period 3 and Post-Randomization (Periods 2 and 3). The total number of events and incidence of participants experiencing AESIs will be tabulated by treatment group and overall for the specified study periods.

For each period, any AESI or SAEs that emerges or worsens during the period of interest will be summarized:

- Adverse Events of Special Interest,
- Serious AE,
- Related AESIs – defined as those judged by the investigator to be ‘possibly’, ‘probably’ or ‘definitely’ related
- Related SAEs – defined as those judged by the investigator to be ‘possibly’, ‘probably’ or ‘definitely’ related
- AE leading to trial medication discontinuation
- AE leading to trial discontinuation – defined as a request by the participant to withdraw from future follow-up visits

Note: Clinical laboratory values noted as out of range at Week 4 that were also noted as out of range at screening will not be considered emergent AESI.

Summaries of AESI and SAEs occurring during the Randomized Period will include risk differences with 95% CI, computed using the Newcombe hybrid score method (with continuity correction; DOI: 10.1177/0962280211415469), to evaluate each GMRx2 dose levels against Placebo. Risk differences will also be computed between GMRx2 dose levels for exploratory comparison. System organ classes and preferred terms with events occurring in at least 1% of the sample will be included.

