3.11.2 Laboratory Parameters: Hematology, Biochemistry & Urine

Blood hematology, biochemistry and urine parameters will be collected according to the schedule of events. Only scheduled visit results will be presented in summary tabulations. Unscheduled visits will be included in data listings only. The baseline value for each parameter will be the latest non-missing value recorded before randomization (i.e., prior to Period 2).

Estimated Glomerular Filtration Rate (eGFR) results provided by the various pathology laboratories across study may be calculated by different equations; however any differences are expected to be balanced across randomized treatment groups and no adjustments will be made.

Actual values and changes from baseline for all laboratory parameters will be descriptively summarized by treatment group. A subset by-participant listing of out-of-range values will be presented.

In addition, tabular descriptive summaries will present the number and percentage of participants at Week 4 with:

- serum sodium concentration below 135 mmol/l
- serum sodium concentration above 145 mmol/l

- serum potassium concentration below 3.5 mmol/l
- serum potassium concentration above 5.5 mmol/l
- serum sodium <135mmol/l or >145 mmol/l, and/or serum potassium <3.5 mmol/l or >5.5mmol/l at week 4
- eGFR (estimated GFR) drop of over 30% from baseline

Frequencies and proportions, including frequency of missing data will be presented. Risk differences with 95% CI, computed using the Newcombe hybrid score method (with continuity correction), to evaluate GMRx2 dose levels against Placebo will be performed. The analysis of binary secondary safety endpoints will be performed on the Safety Analysis Set, limited to those participants who were randomized. Participants will be grouped as treated.

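### The SAP's AESI definition omits headache and narrows peripheral edema relative to protocol 17.1.2; the missing-data rule for the two orthostatic safety outcomes also needs correcting

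*SAP*

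**What the plan says.** **AESI definition.** Protocol 17.1.2 lists five categories of AESI, two of which are headache and "Peripheral edema". Protocol 17.1.1 and 17.2.3 limit collection of non-serious events to AESIs. SAP 3.11.1.1 makes the same restriction ("The only non-serious Adverse Events to be recorded are Adverse Events of Special Interest") but lists four categories. Headache is not among them, and the edema item reads "Symptom of pedal edema reported by the participant". SAP 2.6.2, on changes in planned analysis, does not mention the AESI list. The revision history of SAP 2.0 says that the document was aligned with protocol version 6.0.

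**Use of the definition.** SAP 3.11.1.2 tabulates AESIs by arm, with risk differences and 95% confidence intervals for each dose against placebo.

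**Orthostatic outcomes.** SAP 2.4.2.2 lists orthostatic hypotension and hypertension at Week 4 as secondary safety outcomes. SAP 3.10.3.2 analyses them alongside the clinic BP control endpoints: complete-case summaries first, then a GEE in which missing Week 4 values become 'failures'.

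**Laboratory note.** SAP 3.11.1.2 says that "any AESI or SAEs that emerges or worsens during the period of interest will be summarized", and for an event ongoing at randomization that then worsens, "the AE worsening will be allocated to the Period 2 treatment". A note adds that laboratory values "out of range at Week 4 that were also noted as out of range at screening will not be considered emergent AESI".

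**The concern.** Because no other non-serious events are recorded, the AESI list decides which of them reach the comparative safety tables. Two documents that should agree give different lists, and the later one records no decision to differ. Edema is not a marginal category here: protocol 5.7 names peripheral edema as the most common adverse effect of amlodipine and argues that the other two components reduce it. Headache could be more or less frequent on active treatment than on placebo, so its omission could move the any-AESI difference either way. That is a reason to settle the list while the data are blind.

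The orthostatic rule is a smaller matter of the same kind. 'Failure' has a clear meaning for BP control, where the endpoint is desirable. For a harm it could mean that the event occurred or that it did not, and the SAP does not say which.

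**Working it through.** **1. The two AESI lists side by side**

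| Category | Protocol 17.1.2 | SAP 3.11.1.1 |
|---|---|---|
| Symptoms possibly due to hypotension | listed | listed |
| Abnormalities in named laboratory tests | listed | listed, same tests |
| Headache | listed | absent |
| Edema | "Peripheral edema" | "Symptom of pedal edema reported by the participant" |
| Other symptom or laboratory abnormality that ended treatment | listed | listed |

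Three categories match in substance, one is narrower in the SAP and one is missing. Under the SAP list, a non-serious headache is an AESI only if it is possibly related to hypotension or led to withdrawal. Staff-observed or non-pedal edema likewise falls outside the list unless another category catches it.

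**2. Possible effect on the any-AESI difference**

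The documents give no event rates, so every input here is assumed. Other AESIs occur in b = 15% on active and 10% on placebo, and headache at rate h occurs independently of them. P(any AESI) = 1 − (1 − b)(1 − h).

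- Without headache: 15% − 10% = 5.0 points.
- h = 3% versus 6%: 1 − 0.85 × 0.97 = 17.55%; 1 − 0.90 × 0.94 = 15.40%; difference 2.15 points.
- h = 5% versus 5%: 1 − 0.85 × 0.95 = 19.25%; 1 − 0.90 × 0.95 = 14.50%; difference 4.75 points.
- h = 8% versus 4%: 1 − 0.85 × 0.92 = 21.80%; 1 − 0.90 × 0.96 = 13.60%; difference 8.2 points.

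For scale, at the planned 100 versus 50 the approximate 95% half-width around the 5.0-point difference is 1.96 × √(0.15 × 0.85/100 + 0.10 × 0.90/50) = 10.9 points.

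**3. Orthostatic outcomes: what 'failure' codes**

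The SAP's only gloss, in 3.10.1.2, is that a participant with a missing value has not achieved the endpoint. It was written for the secondary efficacy endpoints. Taken literally for a harm, it codes missing as no event. SAP 3.10.3.1 models the occurrence of the event, which fits that reading. The ordinary sense of failure for a harm would be an event.

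Let pA and pP be the event rates among those observed, and mA and mP the missing rates.

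- Missing = no event: RD₀ = (1 − mA)pA − (1 − mP)pP.
- Missing = event: RD₁ = RD₀ + (mA − mP).

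The two readings therefore differ by exactly the between-arm difference in missingness. With assumed pA = 6% and pP = 3% (complete-case difference 3.0 points):

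| Missing, active / placebo | RD₀ | RD₁ |
|---|---|---|
| 8% / 3% | 5.52 − 2.91 = 2.61 | 7.61 |
| 3% / 8% | 5.82 − 2.76 = 3.06 | −1.94 |
| 5% / 5% | 5.70 − 2.85 = 2.85 | 2.85 |

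These are crude risk differences, not GEE-adjusted ones. Under the no-event reading the rate falls in every arm with missing data, while the difference moves by at most about 0.4 points (3.0 − 2.61).

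**4. Analysis set**

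SAP 3.10.3.1 puts the GEE on the Randomized Set, and 3.10.3.2 applies the same method to clinic endpoints. SAP 3.11.2 puts binary secondary safety endpoints on the Safety Set, limited to randomized participants, as treated. The Safety Set (3.4.2) includes anyone who took a run-in dose, and randomization requires 80–120% run-in adherence (protocol 8.2.1). The two sets therefore hold almost the same people, and in practice only as-treated grouping separates them.

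**5. Laboratory note**

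The note makes no exception for a value that worsened or changed direction. It refers to screening, whereas 3.11.2 says "The baseline value for each parameter will be the latest non-missing value recorded before randomization". Protocol Table 5 schedules one set of study bloods before randomization, at screening or during run-in, so the two references will normally coincide.

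**The case against.** The best defence is that nothing is lost. The protocol governs collection, so headache and all peripheral edema should be recorded as AESIs. No step in the SAP filters recorded AESIs against its own list, so a programmer working from the recorded AESI data would tabulate headache anyway. The edema wording may also matter little: protocol 17.2.3 collects AESIs by asking participants, and protocol 8.4.3 itself speaks of pedal oedema. The illustrated shifts of about three points are well inside a half-width of about 11 points. For the orthostatic outcomes, complete-case proportions, risk differences and missing counts are already planned.

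Much of this stands. It makes the harm conditional on the SAP definition being applied as written, and it makes edema the weaker half of the mismatch. It does not remove the conflict. A safety table should not depend on the programmer setting aside the SAP's definition, and the width of an interval does not justify using the wrong event list.

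Some stronger inferences are tempting but not supported:

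- *Headache data were never collected.* Protocol 17.1.2 requires their collection.
- *The laboratory note contradicts its own section and hides worsening.* It can be read as limiting only what counts as newly emerging, leaving the worsening rule intact. SAP 3.11.2 also provides that "Actual values and changes from baseline for all laboratory parameters will be descriptively summarized by treatment group".
- *The orthostatic risk difference could change by five points or reverse sign.* That needs the less likely coding of missing as an event and an assumed five-point imbalance in missingness.
- *The two analysis sets differ materially.* They hold almost the same participants.

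**Conclusion.** The AESI list mismatch is established by the text alone and should be corrected. Followed literally, SAP 3.11.1.1 yields AESI tables and risk differences that do not match the protocol's definition. The direction and size of the effect cannot be known from the documents; the range of 2.15 to 8.2 points around 5.0 is illustrative and rests on assumed rates and independence.

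The orthostatic rule is a secondary correction. On the likelier reading it slightly understates the rate of a harm, and in the scenarios shown it moves the risk difference by no more than about 0.4 points. The case for correcting it is that an efficacy convention has been applied to a safety outcome without saying what it codes.

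The laboratory note calls for clarification only. The primary efficacy endpoint, the primary safety endpoint, SAEs and the Week 4 sodium, potassium and eGFR tables are unaffected.

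**What to change.** 1. **Main change.** Before unblinding, replace the list in SAP 3.11.1.1 with the list in protocol 17.1.2, so that headache and peripheral edema without restriction enter the AESI tables and risk differences.
2. **Secondary change.** In SAP 3.10.3.2, exclude orthostatic hypotension and hypertension from the missing = 'failures' rule. Run their GEE on observed cases, consistent with the complete-case summary already planned, and report missing counts by arm. Name one analysis set for them, reconciling 3.10.3.1 and 3.10.3.2 with 3.11.2.
3. **Clarification.** State in SAP 3.11.1.2 that the laboratory note does not exclude values that worsened or changed direction from the 3.11.2 baseline.

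The cost is SAP wording and table programming. No new data are needed, because the protocol already collects these events. AESI counts may rise in every arm.

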3.11.1.2 Adverse Event Summaries

For the summary of safety parameters, AEs will be classified according to the treatment period and treatment received as of the start date of the AE (Section 3.5.3). If an AE is ongoing at the time of randomization, it will be allocated to the Period 1 treatment. If a treatment ongoing at randomization worsens following randomization, the AE worsening will be allocated to the Period 2 treatment.

AESIs and SAEs will be classified according to the MedDRA (Medical Dictionary for Regulatory) system (version 24.0, March 2021) and summarized by system organ class and preferred term.

Treatment periods for AE summary include: Period 1/Run-in Period, Period 2, Period 3 and Post-Randomization (Periods 2 and 3). The total number of events and incidence of participants experiencing AESIs will be tabulated by treatment group and overall for the specified study periods.

For each period, any AESI or SAEs that emerges or worsens during the period of interest will be summarized:

- Adverse Events of Special Interest,
- Serious AE,
- Related AESIs – defined as those judged by the investigator to be ‘possibly’, ‘probably’ or ‘definitely’ related
- Related SAEs – defined as those judged by the investigator to be ‘possibly’, ‘probably’ or ‘definitely’ related
- AE leading to trial medication discontinuation
- AE leading to trial discontinuation – defined as a request by the participant to withdraw from future follow-up visits

Note: Clinical laboratory values noted as out of range at Week 4 that were also noted as out of range at screening will not be considered emergent AESI.

Summaries of AESI and SAEs occurring during the Randomized Period will include risk differences with 95% CI, computed using the Newcombe hybrid score method (with continuity correction; DOI: 10.1177/0962280211415469), to evaluate each GMRx2 dose levels against Placebo. Risk differences will also be computed between GMRx2 dose levels for exploratory comparison. System organ classes and preferred terms with events occurring in at least 1% of the sample will be included.

In addition, the frequency and percentage of participants discontinuing treatment due to an AE will be reported with risk differences between treatment groups computed using the Newcombe hybrid score method (with continuity correction) to evaluate the primary safety endpoint among GMRx2 dose levels versus Placebo. Risk differences will also be computed between GMRx2 dose levels for exploratory comparisons.

3.11.2 Laboratory Parameters: Hematology, Biochemistry & Urine

Blood hematology, biochemistry and urine parameters will be collected according to the schedule of events. Only scheduled visit results will be presented in summary tabulations. Unscheduled visits will be included in data listings only. The baseline value for each parameter will be the latest non-missing value recorded before randomization (i.e., prior to Period 2).

Estimated Glomerular Filtration Rate (eGFR) results provided by the various pathology laboratories across study may be calculated by different equations; however any differences are expected to be balanced across randomized treatment groups and no adjustments will be made.

Actual values and changes from baseline for all laboratory parameters will be descriptively summarized by treatment group. A subset by-participant listing of out-of-range values will be presented.

In addition, tabular descriptive summaries will present the number and percentage of participants at Week 4 with:

- serum sodium concentration below 135 mmol/l
- serum sodium concentration above 145 mmol/l

- serum potassium concentration below 3.5 mmol/l
- serum potassium concentration above 5.5 mmol/l
- serum sodium <135mmol/l or >145 mmol/l, and/or serum potassium <3.5 mmol/l or >5.5mmol/l at week 4
- eGFR (estimated GFR) drop of over 30% from baseline

Frequencies and proportions, including frequency of missing data will be presented. Risk differences with 95% CI, computed using the Newcombe hybrid score method (with continuity correction), to evaluate GMRx2 dose levels against Placebo will be performed. The analysis of binary secondary safety endpoints will be performed on the Safety Analysis Set, limited to those participants who were randomized. Participants will be grouped as treated.

Appendix 1: List of Abbreviations

Abbreviation	Definition
AE	Adverse Event
AESI	Adverse Event of Special Interest
ATC	Anatomical Therapeutic Chemical
BP	Blood Pressure
CI	Confidence Interval
cm	Centimeters
CRO	Contract Research Organization
DBP	Diastolic Blood Pressure
ECG	Electrocardiogram
eGFR	estimated Glomerular Filtration Rate
EOT	End of Trial
EU	European Union
FAS	Full Analysis Set
FCS	Fully Conditional Specification
FDA	USA Food & Drug Administration
GEE	Generalized Estimating Equation
GM	George Medicines
GMRx2	Single pill combinations of telmisartan/amlodipine/indapamide
ICH	The International Conference
LOCF	Last Observation Carried Forward
LS	Least Square
MedDRA	Medical Dictionary for Regulatory Activities
MI	Multiple Imputation
mg	Milligram
MMRM	Mixed Model for Repeated Measures
mmHg	Millimeters of Mercury
(Q1-Q3)	Interquartile limits
RCT	Randomized Controlled Trial
RR	Risk ratio
SAE	Serious Adverse Event
SAP	Statistical Analysis Plan
SAS	Statistical Analysis Software
SBP	Systolic Blood Pressure
SD	Standard deviation
SOC	System Organ Class
STEAE	Serious Treatment-Emergent Adverse Event
TE	Treatment-Emergent
USA	United States of America
WHO	World Health Organization

Appendix 2: Schedule of Assessment

Visit Name	PRE-SCREEN (Optional)	SCREEN (Run-in start) ⁷	RAND (Run-in end)	FU1 (End of trial medication)	EOT ⁵ (Telephone safety FU)
Visit Week	Week -4	Week -2		Week 4	Week 8
Visit Day (Visit window days)	-28	-14 (-12 to -21)*		28 (±7)*	56 (±7)*
Written informed consent ¹	✓	✓			
Eligibility (inclusion & exclusion)	✓	✓	✓		
Medical history	✓	✓			
Physical examination ²		✓			
Demographics		✓			
Anthropometrics – Height, weight		✓			
Clinic BP, standing BP, pulse		✓	✓	✓	
12-lead electrocardiogram (ECG)		✓			
Cardiovascular risk assessment		✓			
Dispensing of home BP monitor		✓			
Home BP monitoring			→		
Home BP monitor brought to clinic			✓	✓	
24-hour ambulatory BP measurement if participating in substudy				✓	
Blood Collection					
Study bloods ³		✓		✓	
Follow-up creatinine with eGFR ⁴					✓ ⁴
Pregnancy test if childbearing potential		✓			
Blood sample for storage for substudy		✓		✓	
Urine Collection³					
Albumin-creatinine ratio		✓		✓	✓ ⁴
Urine sample for storage for substudy		✓		✓	✓ ⁴
Medications					
Discontinue BP lowering medication (if applicable)	✓	✓			
Dispensation of run-in medication		✓			
Allocation of randomized trial medication			✓		
Dispensation of trial medication			✓		
Return of trial medication			✓	✓	
Adherence to trial medication			✓	✓	
Review of concomitant medications	✓	✓	✓	✓	✓
Safety					
AEI or SAE			→		

¹ At Screening visit, if not collected previously. Written informed consent may be collected at pre-screening.

² Systems-based examination deemed necessary for the safety of participants by the site investigator

³ The following blood and urine tests should be taken at a time most suitable for the participant at Screening visit or during run-in so that results are available for review at the RAND visit and during week 4 (ie. at the week 4 final visit or in the preceding week):

- Fasting glucose
- Fasting lipid profile (total cholesterol, low-density lipoprotein cholesterol, high-density lipoprotein cholesterol)
- HbA1c - for participants with diabetes without a HbA1c in past 3 months; repeat measure not required at week 4
- Complete blood count (red blood cell count, hemoglobin, hematocrit, mean corpuscular volume, reticulocyte count, white blood cell count, platelet count)
- Liver function (bilirubin, albumin, total protein, gamma-glutamyl transferase, alkaline phosphatase, aspartate transaminase and alanine transaminase)

- Sodium, potassium, chloride
- Calcium
- Creatinine with eGFR
- Uric acid
- Thyroid-stimulating hormone; repeat measure not required at week 4
- Blood sample for storage for substudy (if participating)
- Urine albumin-creatinine ratio
- Urine sample for storage for substudy (if participating)

All laboratory investigations and ECG will be performed at the trial site based local laboratory. If blood test results are not available on the same day as the randomization visits, once eligibility has been confirmed, participants may need to return to the clinic to collect the trial medication and home BP monitor. Alternatively, where feasible and consent from the participant received, trial medication and home BP monitor may be couriered to the participant's home once eligibility is confirmed.

⁴At Week 8, only for participants who have had $\geq 30\%$ reduction in eGFR and/or $\geq 30\%$ increase in serum creatinine between RAND and week 4 visits

⁵If participating in Open-Label extension phase, see protocol for additional assessments at week 4 and thereafter

* If a screening visit is rescheduled, then the randomization date should be scheduled/rescheduled so that the length of the run-in period remains at least 12 days. Option to extend run-in by up to 1 week if there have been technical or administrative issues with BP machine use and or measurement protocol. Ideally there should not be a gap between the end of Run-in period and Randomization. Post-randomization visit dates should not be altered i.e. should remain at the scheduled time since randomization.

EOT=End of trial; FU=Follow up; PRESCREEN=Pre-screening; RAND=Randomization; SCREEN=Screening

